Cover Page

Improving Delivery of Patient-Centered Cardiac Rehabilitation

NCT02105246

August 11, 2018

Study Protocol

Background

Ischemic heart disease (IHD) is the leading cause of death in Veterans and has been identified as a priority condition for improving healthcare within the VA. Exercise-based cardiac rehabilitation (CR) is an evidence based, cost effective therapy that reduces morbidity and mortality following acute myocardial infarction (MI), coronary artery bypass grafting (CABG) or percutaneous coronary intervention (PCI). The American Heart Association (AHA) and American College of Cardiology (ACC) recommend referral to CR as one of its 9 performance measures for secondary prevention (along with aspirin, beta blockers, statins and smoking cessation) in patients with IHD. Unfortunately, despite the compelling benefits and widespread endorsement of its use, CR is vastly underutilized in VHA. A recent Presidential Advisory from the AHA concluded, "The remarkably wide treatment gap between scientific evidence of the benefits of cardiac rehabilitation and clinical implementation is unacceptable." Only 35 (27%) of VA facilities offer CR programs, and less than 10% of eligible veterans receive this guideline-recommended therapy. Geographic distance is by far the largest barrier to participation. Of the 9.2 million veterans currently enrolled in VHA, 6.7 million (73%) live more than 60 minutes from a VA CR center [based on geography data from VA Planning Systems Support Group (PSSG)]. Thus, there is an urgent need to adapt CR programs to improve access to and utilization of CR among rural veterans.

In a recent study conducted at the Iowa City VA (Wakefield et al, 2014), 48 patients completed a home-based program and 12 patients completed face-to-face CR. There was no difference in blood pressure, lipid levels, weight, glycosylated hemoglobin or rate of rehospitalization between the two groups. Home-based CR participants were highly satisfied with their care and had a better completion rate than patients who underwent face-to-face CR (89% vs. 73%). Costs for home and center-based CR programs were comparable. These findings suggest that a home-based CR program is a viable, safe, and cost- effective alternative to center based programs. In a 2010 Cochrane review, there was no significant difference in mortality among patients randomly assigned to home-based CR vs. center-based CR.

Objectives

Test the hypothesis that patients undergoing home based cardiac rehabilitation will not differ in 6 minute walk time, physical activity, quality of life, patient and caregiver satisfaction, and re-hospitalization as compared with patients undergoing center-based cardiac rehabilitation.

Aim 1. Determine whether automatic referral to home- vs. center-based CR increases patient participation in CR after hospitalization for myocardial infarction or coronary revascularization.

Aim 2. Among patients who choose to participate in CR, compare the effectiveness of home- vs. center-based CR on six-minute walk distance, quality of life, and healthcare expenditures.

Aim 3: Determine whether the effects of home vs. center-based CR differ by age, gender, race, ethnicity, distance from medical center, employment, socioeconomic status, social support, caregiver status, comorbid conditions, or patient preference.

Study Design

Cardiac rehabilitation involves exercise training, education, and lifestyle counseling for patients with cardiac conditions. Home and center-based cardiac rehabilitation programs, if followed by patients, are equally effective in their benefits on risk factors, health-related quality of life, death, and clinical events following acute myocardial infarction or coronary revascularization. This study will compare the effectiveness of existing cardiac rehabilitation programs. The San Francisco VA Medical center offers a home-based (but not a center based) cardiac rehabilitation program to patients who are hospitalized for myocardial infarction, percutaneous coronary intervention, or coronary artery bypass grafting. The other study sites offer a center-based (but not a home-based) cardiac rehabilitation to the same group of patients. All facilities have initiated a comprehensive CR intervention with 7 components:

1. Educate and engage stakeholders (grand rounds, posters, brochures, one-on-one meetings)
2. Automate referrals

3. Standardize templates and stop codes for consults, progress notes, exercise prescription, and the patients' Individualized Treatment Plans
4. Use database to track all patients referred; monitor % enrolled, number of sessions completed.
5. Standardize outcome assessment
6. For CABG patients, provide in-hospital assessment and phase I cardiac rehabilitation; coordinate care with home PT
7. Offer a phase II cardiac rehabilitation program within 6 months of hospitalization.

The only difference between the sites is that San Francisco offers a home-based cardiac rehab program and other sites will offer a center-based cardiac rehab program. Research outcomes will include processes of care (% of eligible patients referred, % enrolled, average number of sessions completed, provider knowledge) and patient outcomes (6 minute walk distance, physical activity, quality of life, patient and caregiver satisfaction, rehospitalization, mortality). The study will evaluate the effectiveness of each CR program on these outcomes. In addition, research participants will be asked to participate in a total of 3 additional study visits. The visits will take place 3 months, 6 months, and 12 months after their enrollment in the cardiac rehabilitation program. Medical records will be reviewed and death certificates will be obtained for up to 10 years of follow-up.

Statistical Analysis Plan

The outcomes listed will be measured at baseline, and then at 3, 6, and 12 months following first visit to CR. Prior to inferential statistics, we will use descriptive statistics and graphs to explore distributions, univariate outliers, and basic bivariate associations with home- vs. center-based CR. We will then compare baseline characteristics of the two groups to examine differences on key subgroup variables including age and type of procedure resulting in the need for CR. Imbalanced baseline measures will be included as covariates in outcome analyses. To appropriately model these nested data, we will use linear mixed models also called multilevel or hierarchical linear models. Our primary outcomes on which only the patient or their caregiver provide data will be analyzed using a multivariate regression model with a simple random -effects structure with repeated-measures. We anticipate that patients who agree to enroll in home-based CR will be different than those who agree to enroll in center- based CR. Therefore, we will use other variables measured at baseline to construct a propensity score for home- vs. center-based CR, and we will adjust the multivariable analyses for this propensity score. Planned subgroup analyses will include the effects of the following predictors on outcomes: age, gender, race/ethnicity, SES, distance to nearest facility that can provide rehabilitation, and presence of caregivers. We will determine whether these same socio-demographic factors are associated with patient preference. We will also conduct subgroup analyses where we have identical measures from patients and caregivers.

Study Application (Version 1.14)

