11.0 Scientific Considerations

11.1 Hypothesis (Help Text updated 9/13):

This study has a hypothesis:

Yes No

If yes, state the hypothesis or hypotheses:

Patients undergoing home based cardiac rehabilitation will not differ in 6 minute walk time, physical activity, quality of life, patient and caregiver satisfaction, and re-hospitalization as compared with patients undergoing center-based cardiac rehabilitation.

11.2 * List the specific aims:

Aim 1. Determine whether automatic referral to home- vs. center-based CR increases patient participation in CR after hospitalization for myocardial infarction or coronary revascularization.

Aim 2. Among patients who choose to participate in CR, compare the effectiveness of home- vs. center-based CR on six-minute walk distance, quality of life, and healthcare expenditures.

Aim 3: Determine whether the effects of home vs. center-based CR differ by age, gender, race, ethnicity, distance from medical center, employment, socioeconomic status, social support, caregiver status, comorbid conditions, or patient preference.

11.3 Statistical analysis:

The outcomes listed will be measured at baseline, and then at 3 and 6 months following first visit to CR. Prior to inferential statistics, we will use descriptive statistics and graphs to explore distributions, univariate outliers, and basic bivariate associations with home- vs. center-based CR. We will then compare baseline characteristics of the two groups to examine differences on key subgroup variables including age and type of procedure resulting in the need for CR. Imbalanced baseline measures will be included as covariates in outcome analyses.

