13.0 Sample Size and Eligibility

13.1 Number of subjects that will be enrolled at UCSF and affiliated institutions:

200

13.2 Total number of subjects that will be enrolled at all sites (Help Text updated 9/13):

400

13.3 Estimated number of people that you will need to consent and screen here (but not necessarily enroll) to get the needed subjects:

400

13.4 Explain how and why the number of subjects was chosen (Help Text updated 9/13):

Sample size estimation for the difference between two groups over four assessments assuming a linear trend. The estimate is based on a two-sided alpha of .05, power of .90, a constant correlation of 0.5 among all repeated measurements, and a 5% overall attrition. San Francisco will enroll 200 participants while the other centers will enroll 100 participants each with a study total of 400 participants. With these assumptions, a composite effect of .5 can be detected

13.5 * Eligible age range(s):

- 0-6 years
- 7-12 years
- 13-17 years
- 18+ years

13.6 Inclusion criteria:

- CABG within 6 months prior to first session
- PCI within 6 months prior to first session
- Acute MI within 6 months prior to first session

13.7 Exclusion criteria:

- Age < 18 years
- Pregnant
- Behavioral or cognitive limitations that interfere with performing exercise training
- Significant movement disorder that interferes with exercise training
- Blind, deaf or mute
- Homeless (or unstable housing anticipated during the next 3 months)
- LVEF <35% without ICD
- Staged PCI with significant remaining lesion
- Decompensated heart failure
- QTc > 500 msec and no ICD
- 6MWT < 75 m (post-op) or < 150 m (non-surgical)
- Long-term (>30 days) SNF placement
- Atrial arrhythmia not rate controlled
- Mobitz Type II or 3rd degree AV block without pacemaker
- Deceased
- History of unprovoked or exercise-induced VT, VF or syncope with no ICD
- Concerning ventricular ectopy in past 24 hours with no ICD (Lown grading system)
 - Polymorphic/multiform PVCs
 - Couplets, Salvos, or non-sustained VT
 - R on T pattern
 - >10 PVCs per minute

13.8 There are inclusion or exclusion criteria based on gender, race or ethnicity:

Yes No

If **yes**, please explain the nature and rationale for the restrictions:

14.0 Other Approvals and Registrations**14.1 * Do any study activities take place on patient care units:**

Yes No

If **Yes**, attach a letter of support for the study from the involved patient care manager(s).

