- Extremely active (5 or more times/week)

X X X

Typical week during the past month

Frequency **I**ntensity **T**ime

Type

X X X

Number of hours sitting per weekday

X X X

Overall quality of life

X X X

Disease-specific quality of life

X X X

Depressive symptoms

X X X

Anxiety symptoms

X X X

Positive affect

X X X

Servings fruits/vegetables per day

X X X

Smoking

X X X

Alcohol use

X X X

Drug use

X X X

Comorbid medical conditions

X X X

The following table lists all information collected from study subjects for research only. This includes information collected from subject interviews, questionnaires, and other research activities (i.e. the six minute walk test conducted at months 3 and 6). The table also includes the timepoint at which the information is collected.

	Baseline	12 weeks	6 months
Measurements			
6MWT standardized course			
Date	SOC	X	X
Start time (_ : _)	SOC	X	X
End time (_ : _)	SOC	X	X
Total distance (meters? feet?)	SOC	X	X
Peak heart rate	SOC	X	X
O ₂ sat at end of course	SOC	X	X
Max perceived exertion (Borg 1-10)	SOC	X	X
Comments	SOC	X	X
Trails A and B (seconds to complete)	X	X	
Digit symbol (# correct in 120 sec)	X		X
Number of chair stands in 30 sec	X		X
Overall quality of life	X	X	X
Disease-specific quality of life	X	X	X

Satisfaction with health care	X	X	X
Sleep quality	X	X	X
Positive affect	X	X	X
Caregiver communication	X	X	X
Functional status (ADLs, IADLs)	X	X	X
Cardiac self-efficacy	X	X	X
Exercise self-efficacy	X	X	X
Patient Activation	X	X	X
Rate My Plate	X	X	X
Servings fruits/vegetables per day	X	X	X
Grams of saturated fat per day	X	X	X
Medication adherance	X	X	X
Smoking	X	X	X
Other Outcomes			
Days until resume driving		X	
Days until resume intercourse		X	
Days until resume work		X	
Patient (out of pocket) expenses		X	
Knowledge about cardiac disease	X	X	X
Days until rehospitalization	X	X	X
Reason for rehospitalization	X	X	X
Days until death	X	X	X
Cause of death	X	X	X
Tandem Stand Test	X	X	X
Side by side Stand Test	X	X	X
Heel Toe Stand Test	X	X	X

If you have a procedure table, attach it to the submission with your other study documents.

15.2 Interviews, questionnaires, and/or surveys will be administered or focus groups will be conducted:

Yes No

List any standard instruments used for this study:

Trails A and B cognitive function tests
 Digit symbol cognitive function test
 Seattle Angina Questionnaire
 Patient Activation Measure
 International Physical Activity Questionnaire

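### Aim 3 asks whether the home-versus-center effect differs by eleven factors, but the analysis plan names no CR-type-by-factor interaction and its factor list does not match.

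*Combined protocol and SAP*

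**What the plan says.** Aim 3, under Objectives and again in Section 11.2, is to "Determine whether the effects of home vs. center-based CR differ by age, gender, race, ethnicity, distance from medical center". It goes on to employment, socioeconomic status, social support, caregiver status, comorbid conditions and patient preference, which makes eleven factors.

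The Statistical Analysis Plan, repeated in Section 11.3, has one sentence that corresponds: "Planned subgroup analyses will include the effects of the following predictors on outcomes: age, gender, race/ethnicity, SES". It ends with "distance to nearest facility that can provide rehabilitation" and the presence of caregivers. The next sentence is "We will determine whether these same socio-demographic factors are associated with patient preference", which makes preference a dependent variable. The sentence after that concerns measures taken identically on patients and caregivers. No section names an interaction between CR type and a factor, or a contrast between subgroup-specific home-minus-center effects.

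The same text plans linear mixed models adjusted for a propensity score. Section 13.4 sizes the study for a difference between two groups and says nothing about subgroups: "With these assumptions, a composite effect of .5 can be detected".

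**The concern.** Whether the effect of CR type differs by a factor is a question about an interaction. The effect of a factor on the outcome is a different quantity, and either can be present without the other. If the sentence is carried out as worded, a factor that helps or harms both arms equally could be reported as a subgroup finding. A factor that reverses the home-versus-center comparison could go unseen. Separate tests within each subgroup have a related fault: one significant and one non-significant result is common even when the two effects are identical.

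The list mismatch adds to this. An analyst working from the SAP would not know whether comorbid conditions, employment, social support and preference are to be examined as modifiers, or which distance to use. Distance matters here, because the Background calls it by far the largest barrier to participation.

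**Working it through.** **Matching the lists.**

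| Aim 3 factor | In the SAP subgroup sentence? |
|---|---|
| Age; gender; socioeconomic status | Yes |
| Race; ethnicity | Yes, as one combined item |
| Caregiver status | Yes, as presence of caregivers |
| Distance from medical center | Yes, but as distance to the nearest facility able to provide rehabilitation |
| Employment | Not named (may be meant under SES) |
| Social support | Not named (may be meant under caregivers) |
| Comorbid conditions | Not named |
| Patient preference | Not as a modifier; only as a dependent variable |

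That is seven of eleven on a generous count. Interaction terms named: none.

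**The plan's own figure.** Section 13.4 gives 400 in total, 200 of them in San Francisco, with two-sided alpha 0.05, power 0.90, correlation 0.5 and 5% attrition, for a composite effect of 0.5. Reading this as SD units (an assumption, since the scale is not defined), with a difference rising linearly from 0 to 0.5 over four equally spaced visits:

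- n per arm = 2 × 3.2415² × 0.9 / 0.5² = 75.7. Here 3.2415 = 1.960 + 1.2816, and 0.9 = (1 − 0.5) × 20 / (10/3)² is the variance of the fitted end difference.
- Total = 2 × 75.7 / 0.95 = about 160.

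This does not reproduce 400. Because the composite effect is undefined, that does not show 400 to be wrong. On this reading 400 is ample for the main comparison.

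**Assumptions for the rest** (not in the documents): SD units; a binary factor with share *f* at one level, equal in both arms; 190 per arm (200 less 5%); no inflation for clustering or propensity adjustment. Correlation 0.5 is from Section 13.4.

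**Literal predictor test against interaction test.** Change from baseline to 6 months, *f* = 0.5. Variance of change = 2(1 − 0.5) = 1.

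- Predictor SE, pooled over arms = √(4/380) = 0.1026.
- Interaction SE = √[(2/190)(1/*f* + 1/(1 − *f*))] = 0.2052.

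| True situation | Predictor test significant | Interaction test significant |
|---|---|---|
| Factor shifts change by 0.5 SD equally in both arms | 99.8% | 5% |
| Home minus center is +0.25 SD at one level, −0.25 SD at the other | 5% | 68% |

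**Separate within-subgroup tests, same true effect in both subgroups.** With *p*₁ and *p*₂ the powers in the two subgroups (SE = √(2/(190*g*)) for a subgroup with share *g*), the chance that exactly one is significant is *p*₁(1 − *p*₂) + *p*₂(1 − *p*₁).

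| True effect in both | 50:50 | 25:75 | 10:90 |
|---|---|---|---|
| 0 | 9.5% | 9.5% | 9.5% |
| 0.3 SD (illustrative) | 50% | 58% | 70% |
| 0.5 SD | 13% | 32% | 66% |

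**Precision of the interaction depends on the contrast.** Section 11.3 says "The outcomes listed will be measured at baseline, and then at 3 and 6 months following first visit to CR", the SAP adds 12 months, and Section 13.4 assumes four assessments with a linear trend. For *f* = 0.5, the interaction detectable with 90% power is 3.2415 × √(8*v*/190), where *v* is the variance of the contrast:

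| Contrast | *v* | Detectable | Power for 0.5 SD |
|---|---|---|---|
| Change, baseline to 6 months | 1.00 | 0.67 SD | 68% |
| Linear trend, four equally spaced visits | 0.90 | 0.63 SD | 73% |
| 6-month value adjusted for baseline | 1 − 0.5² = 0.75 | 0.58 SD | 80% |
| Mean of 3 and 6 months adjusted for baseline | 0.75 − 0.25 = 0.50 | 0.47 SD | 93% |

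Uneven splits are less precise. The change contrast gives 0.77 SD at 25:75 and 1.11 SD at 10:90. An assumed variance inflation of 1.25 to 1.5 from adjustment moves its 50:50 figure from 0.67 to between 0.74 and 0.81 SD.

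**The case against.** The strongest reply is that in a two-arm comparison subgroup analysis ordinarily means the arm effect by subgroup, and Aim 3 already states that question. A reader might infer from the sentence that the investigators intend main effects only. The documents do not establish that, and the 99.8% and 5% figures describe only the literal reading. What stands against the plan is narrower: no term or contrast is named, and the two analyses the wording most readily suggests would not answer the aim.

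A reader might also infer that four factors have been dropped. The sentence says only what the analyses will include, so the list may not be exhaustive, and employment and social support may sit under broader items. The clearest gaps are comorbid conditions and preference as a modifier.

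Three further readings go too far.

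- Adding the interaction does not fully answer Aim 3. Under Study Design all home patients come from San Francisco, so CR type by factor cannot be separated from San Francisco by factor.
- No single detectable interaction describes this study; the figure depends on a contrast the plan has not fixed.
- Expenditures cannot be said to lack a baseline value. The Section 15.1 table marks "Patient (out of pocket) expenses" at one timepoint, but Aim 2 is to "compare the effectiveness of home- vs. center-based CR on six-minute walk distance, quality of life, and healthcare expenditures". The documents do not equate the two or say that earlier expenditure is unavailable.

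**Conclusion.** The point holds as a mismatch between a stated aim and its analysis. Aim 3 asks about effect modification; the SAP names no interaction, lists seven of the eleven factors on a generous count, and words distance differently. This rests on the text alone and needs no assumption. It should be corrected, but it leaves the main home-versus-center comparison untouched, and sizing the study for that comparison alone is acceptable.

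The error rates above illustrate what could go wrong under either reading of the sentence. They rest on SD units, 190 per arm, equal prevalence in both arms and no clustering. Under those assumptions the detectable interaction for a 50:50 factor is about 0.47 to 0.67 SD depending on the contrast, before any inflation for propensity adjustment or clustering. A reader might take this to mean that the study is too small; the documents make no claim of power for Aim 3, so the conclusion is only that its estimates will be imprecise.

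**What to change.** Replace the subgroup sentence in the Statistical Analysis Plan and Section 11.3 with:

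> For each Aim 3 factor measured at baseline we will add a CR-type-by-factor interaction (with visit, for repeatedly measured outcomes) to the propensity-adjusted model used for that outcome, including the models for rehospitalization, mortality and expenditures. We will report the interaction estimate with its 95% CI, and home minus center by factor level or at stated values of continuous factors. We will not infer effect modification from predictor main effects or from separate within-subgroup p-values.

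In addition:

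- Use one factor list and one distance definition in Aim 3 and the SAP. Add comorbid conditions, which the Section 15.1 clinical table collects at baseline. For employment, social support and preference, either add them or, if no baseline source exists, remove them from Aim 3.
- State that all home patients come from one site, so CR type by factor cannot be separated from San Francisco by factor.
- State that the study is sized only for the main comparison and that the Aim 3 estimates will be imprecise. Do not write detectable-interaction figures into the SAP.

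The cost is SAP wording, a little more modelling and a check of the baseline source of each factor. No extra patients or visits are needed. The downside is visibly wide subgroup intervals: for the 6-month change contrast, half-widths of about 0.40, 0.46 and 0.67 SD at 50:50, 25:75 and 10:90 (1.96 times the SEs 0.2052, 0.2369 and 0.3420).
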